## 14.3 Swimlane Plots

A swimlane plot displaying some key radiological milestones will be produced, color-coded by planned dose level. Time in weeks will be displayed along the horizontal axis, and subject ID along the vertical axis. Subjects will be arranged from top to bottom in descending order of follow-up time. For each subject, the time from treatment start until end of follow-up will be represented by a horizontal bar. In addition, there will be different symbols to mark the following events: confirmed CR, confirmed PR, ongoing SD, PD, end of treatment, and death.

## 15 Safety Analyses

The subsections in this section include specifications for summarizing safety endpoints that are common across clinical studies such as adverse events (AEs), laboratory tests and vital signs.

Safety analyses will be done on the Safety Analysis Set, unless otherwise specified.

### 15.1 Dose Limiting Toxicities

The occurrence of dose limiting toxicities (DLTs) during the DLT evaluation period (i.e., during the first treatment cycle of 28 days) is a primary endpoint of this study. The DLT set will be used for the analysis of the primary endpoint. Please refer to [Section 6.2.4](#) of the Clinical Study Protocol MS201408-0005 for the detailed definition of a DLT.

The number and proportion of subjects experiencing DLTs will be reported by dose level. Posterior probabilities (2.5%, 25%, 50%, 75%, and 97.5% quantiles) for a DLT by tested dose level will be estimated using the BLRM specified in the protocol.

Details of the DLTs will be presented in a listing sorted by SOC and PT, including: DLT, SOC, PT, relationship to M4112, seriousness, dose group, time since last and first administration of M4112, and subject's age/sex/site of primary tumor.

In addition, a DLT profile plot of all subjects in the Safety Analysis Set will be produced. This will show a closed square for all subjects who were considered evaluable (in DLT set) and did not have a DLT during Cycle 1, an open square for those who experienced a DLT during Cycle 1, and an open circle for those who were excluded from the DLT Set. This plot will have Cohort Number on the x-axis and dose level (mg) on the y-axis.

### 15.2 Adverse Events

The severity of AEs will be graded using the NCI-CTCAE v4.03. If a particular AE's severity is not specifically graded by this guidance, the Investigator uses the general NCI-CTCAE definitions of Grade 1 through Grade 5 following his or her best medical judgment. The latest MedDRA version at the time of data cut-off will be used to code AEs according to System Organ Class (SOC) and Preferred Term (PT).

- **Treatment Emergent Adverse Events (TEAEs)** are events with onset dates occurring during the on-treatment period, or those that worsen in severity during the on-treatment period. All analyses will be based on TEAEs unless otherwise specified.
- **Related Adverse Events** have a relationship to study treatment of “Related” as reported by the Investigator on the Adverse Events CRF page, or unknown (i.e., no answer to the question “Relationship M4112”).
- **Serious Adverse Events (SAEs)** are those recorded on the Adverse Events CRF page as Serious Adverse Event = “Yes”.
- **Adverse Events Leading to Treatment Discontinuation** are those recorded on the Adverse Events CRF page as Action(s) taken with M4112 = “Drug withdrawn”.
- **Adverse Events Leading to Dose Modifications** are those recorded on the Adverse Events CRF page as Action(s) taken with M4112 = “Dose reduced”.
- **Adverse Events Leading to Treatment Interruption** are those recorded on the Adverse Events CRF page as Action(s) taken with M4112 = “Drug interrupted”.
- **Adverse Events Leading to Death** are those recorded on the Adverse Events CRF page as Outcome = “Fatal” as well as AEs of Grade 5.
- **Adverse Events of Special Interest (AESIs)** for M4112 include liver toxicities and immune-related AEs (irAEs) / autoimmune disorders. Any AESI is indicated as such by the Investigator on the Adverse Events CRF page and is also reported as an SAE.

Incomplete AE-related dates will be handled as follows:

- In case the onset date is missing completely or missing partially but the onset month and year, or the onset year are equal to the start of study treatment then the onset date will be replaced by the minimum of start of study treatment and AE resolution date.
- In all other cases the missing onset day or missing onset month will be replaced by 1.
- Incomplete stop dates will be replaced by the last day of the month (if day is missing only), if not resulting in a date later than the date of subject's death. In the latter case the date of death will be used to impute the incomplete stop date.
- In all other cases the incomplete stop date will not be imputed. If stop date of AE is after date of cut-off, outcome of AE is ongoing at cut-off.
- Further information after cut-off (like fatal outcome) might be taken from safety database and included separately into CSR.

### 15.2.1 All Adverse Events

Adverse events will be summarized by worst severity per subject, using MedDRA PT as event category and SOC as summary category, in alphabetical order. If an AE is reported for a given subject more than once during treatment, the worst severity and the worst relationship to study treatment will be tabulated.

There will be a listing of all AEs, sorted by SOC and PT.

The following frequency tables will be prepared, by dose level and overall; in addition, the tables will be provided by PT and primary SOC in alphabetical order:

- Any TEAE
- TEAEs related to M4112
- Any serious TEAEs
- Any nonserious TEAEs
- Any serious TEAEs related to M4112
- TEAEs with NCI-CTCAE severity Grade  $\geq 3$
- TEAEs related to M4112 with NCI-CTCAE severity Grade  $\geq 3$
- TEAEs leading to treatment discontinuation, dose modification, treatment interruption, and death
- TEAEs related to M4112 leading to treatment discontinuation, dose modification, treatment interruption, and death
- AESIs
- TEAEs by SOC and PT

#### **Clinical trial.gov and EudraCT requirements**

Summary tables for nonserious AEs, applying frequency threshold of 5% when excluding SAEs, by SOC and PT, will be provided.

### **15.3 Deaths, Other Serious Adverse Events, and Adverse Events of Special Interest**

#### **15.3.1 Deaths**

The following will be tabulated based on information from the “Death” CRF page.

- Number of deaths
- Number of deaths within 30 days after last dose of M4112
- Number of deaths within 60 days after first dose of M4112
- Reason for death

In addition, date and cause of death will be provided in an individual subject data listing together with selected study treatment information (dose level and date of first / last administration). This listing will also include flags for death within 30 days of last study treatment and death within 60 days of first study treatment, as well as MedDRA coding for AEs with fatal outcome (including those with a toxicity grade of 5 and those with an outcome of “fatal”).

### 15.3.2 Serious Adverse Events

A listing will display all SAEs, sorted by SOC and PT, including: AE, SOC, PT, relationship to M4112, planned dose level, time since last and since first administration of M4112, and subject's age, sex, and race (also see [Section 15.2.1](#)).

### 15.3.3 Adverse Events of Special Interest

A listing of all AESIs will be provided, sorted by SOC and PT, including: AE, SOC, PT, relationship to M4112, planned dose level, time since last and since first administration of M4112, and subject's age, sex, and race (also see [Section 15.2.1](#)).

## 15.4 Clinical Laboratory Evaluation

On-study laboratory assessments are any sample collected after the first administration of any study drug, and within 30 days from last study drug administration.

Laboratory results will be classified according to the NCI-CTC Version 4.03 as provided by the central laboratory. Additional laboratory results that are not part of NCI-CTC will be presented according to the categories: below normal limits, within normal limits and above normal limits (according to the laboratory normal ranges).

The worst on-study grade (from any visit, scheduled or unscheduled) will be summarized considering only subjects with postbaseline laboratory samples: Laboratory tests by NCI-CTC grade (0, 1, 2, 3, 4, any).

Quantitative data will be examined for trends using descriptive statistics (mean, StDev, median, Q1, Q3, minimum, and maximum) of actual values and changes from baseline to each visit over time. Qualitative data based on reference ranges will be described according to the categories (i.e., Low, Normal, and High). The number of subjects with clinical laboratory values below, within, or above normal ranges at baseline compared to endpoint will be tabulated for each test by dose level. Shift tables of baseline versus endpoint (as well as the worst value at any post-baseline visit) will be presented. Abnormalities classified according to NCI-CTCAE toxicity grading version 4.03 will be described using the worst grade. In case of missing data at the end of the treatment period, the last known postbaseline value will be carried forward.

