## Laboratory Values

Laboratory results will be classified by grade according to NCI-CTCAE 4.03. The worst on-treatment grades for chemistry and hematology laboratory results will be summarized. Shifts in toxicity grading from baseline to highest grade during the on-treatment period will be displayed. For laboratory tests without an NCI-CTCAE grade definition, results will be presented categorically (eg, below, within, or above normal limits).

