**Definition of treatment period:**

On-treatment period is defined as the time from the first dose of study treatment through minimum (30 days + last dose of study treatment, start day of new anticancer drug therapy – 1 day).

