## 15.5 Vital Signs

The maximum on-treatment changes from baseline in vital sign measurements will be grouped as indicated in Table 5:

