## 15.7 ECOG Performance Status

The ECOG shift from baseline to highest score during the on-treatment period will be summarized. ECOG performance status with shift from ECOG = 0 or 1 to ECOG = 2 or higher will also be presented in a data listing with subject identifier and other relevant information.

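### The IAP's laboratory tables run to 30 days after last dose without the stop at new anticancer therapy used for its other on-treatment outputs, so values taken on the next treatment can be counted by M4112 dose level

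*SAP*

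**What the plan says.** **General window.** IAP 9, Definition of treatment period, runs from first dose "through minimum (30 days + last dose of study treatment, start day of new anticancer drug therapy – 1 day".

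**Outputs that use it.** IAP 15.2: treatment-emergent adverse events "are events with onset dates occurring during the on-treatment period, or those that worsen in severity during the on-treatment period". IAP 15.5: "The maximum on-treatment changes from baseline in vital sign measurements will be grouped as indicated in Table 5". IAP 15.6 counts potentially clinically significant ECG abnormalities in the on-treatment period. IAP 15.7: "The ECOG shift from baseline to highest score during the on-treatment period will be summarized".

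**Laboratory window.** IAP 15.4: "On-study laboratory assessments are any sample collected after the first administration of any study drug, and within 30 days from last study drug administration". The worst on-study grade draws on scheduled and unscheduled visits alike. Shift tables compare baseline with endpoint "as well as the worst value at any post-baseline visit", and graded shifts go to the worst postbaseline grade. Neither states its own end date, nor does the eDISH plot of peak ALT against peak total bilirubin. The laboratory listing, however, flags the worst on-treatment value.

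**Protocol.** Section 8.5.6, Laboratory Values, plans worst on-treatment grades and adds: "Shifts in toxicity grading from baseline to highest grade during the on-treatment period will be displayed". Treatment-emergent laboratory change is one of the primary endpoints (Protocol 8.3.1, IAP 5.1). IAP 7, which lists departures from the protocol's analyses, does not mention the laboratory window.

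**The concern.** A laboratory value taken after the subject has started another anticancer drug may reflect that drug. IAP 9 recognises this and closes the on-treatment period the day before; IAP 15.4 does not. Followed as written, a cytopenia or transaminase rise first seen on the next treatment can become that subject's worst laboratory grade and be tabulated against an M4112 dose level.

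Two consequences follow. First, part of a primary endpoint would be summarised over a different window from the other components that the IAP summarises on-treatment. Second, IAP 15.4 would be inconsistent with itself, because the value flagged as worst on-treatment in the listing need not be the value behind the worst on-study grade in the table. With three subjects per dose level as the usual cohort, one such value is visible in the results.

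**Working it through.** The plan states no figure to reproduce here. The check compares the windows and then does simple date arithmetic.

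**Inputs**
- On-treatment end: the earlier of last dose + 30 days and the day before new anticancer drug therapy (IAP 9).
- Laboratory end: last dose + 30 days (IAP 15.4).
- Dose-level sizes: four levels of 3 and two of 6 in the protocol's anticipated scenario (Protocol 8.1); 4 × 3 + 2 × 6 = 24, which agrees with the approximately 24 planned.
- s = days from last dose to new therapy. The documents give no values, so s is varied.

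**Excess window**

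On-treatment end = last dose + min(30, s − 1). Excess = 30 − min(30, s − 1), which is 31 − s for s = 1 to 30 and 0 from s = 31.

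| s (days) | On-treatment ends | Laboratory window ends | Excess days |
|---|---|---|---|
| 7 | last dose + 6 | last dose + 30 | 24 |
| 14 | last dose + 13 | last dose + 30 | 17 |
| 21 | last dose + 20 | last dose + 30 | 10 |
| 28 | last dose + 27 | last dose + 30 | 3 |
| 31 | last dose + 30 | last dose + 30 | 0 |

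Illustration: last dose on Day 0, new therapy on Day 10, a Grade 4 neutrophil count first seen on Day 20. The on-treatment period closed on Day 9, so the value is outside it, but it is inside the laboratory window and becomes the worst on-study grade. The excess here is 31 − 10 = 21 days.

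**Weight of one subject**
- Level of 3: 1/3 = 33.3 points.
- Level of 6: 1/6 = 16.7 points.
- All 24: 1/24 = 4.2 points.

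**Chance of at least one affected subject in a level of 3**, if a proportion q of subjects has such a sample (q is assumed): 1 − (1 − q)³ gives 14% at q = 5%, 27% at q = 10% and 49% at q = 20%.

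**After the change.** With the IAP 9 period applied to laboratory data, the excess is 0 days for every s.

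**The case against.** The strongest reply is that the protocol mostly prevents such samples. The synopsis (Follow-up Period and Safety assessments) and Section 7.1.3.2 place safety follow-up, laboratory tests included, before any new anticancer therapy. This stands as a limit on exposure. It does not close the gap: Table 1 footnote d requires the 30 ± 3 day visit of everyone who discontinues, Section 7.1.3.1 puts the End of Treatment Visit before new therapy only where possible, and unscheduled results count towards the worst grade.

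A second reply is that the wider window is defensible. The primary endpoint runs to the last Safety Follow-up Visit, and Protocol 3.4.2.1 warns that immune-related events may first appear after weeks of treatment. An inclusive window could catch a delayed M4112 effect on the liver. This also stands in part, and it shapes the fix, but the IAP does not present the wider window as a deliberate choice.

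Several stronger readings are tempting and are not supported:
- *Every other safety window stops at new therapy.* The 30-day death count (IAP 15.3.1) does not, nor does the adverse-event rule in the separate safety monitoring committee plan (its Section 17.1). The contrast holds for the four outputs named above.
- *The protocol specified the stop and the IAP removed it.* Protocol 8.5.6 says on-treatment but does not define that as ending at new therapy; the rule appears in IAP 9. What went unreported is the move away from on-treatment.
- *The shift tables have no limit.* They state none of their own, but the opening sentence of IAP 15.4 may be meant to govern them.
- *Contaminated samples are certain or common.* The documents give no rate of early switching. The weekly repeat testing in Protocol 7.4.3 begins only after a clinically significant abnormality, so it would not produce the Day 20 sample in a subject with previously normal values.
- *Any disagreement between laboratory and adverse-event tables is an error.* They differ by design, since Protocol 7.4.1.1 makes an abnormal value an adverse event only under stated conditions.

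**Conclusion.** The point holds as an inconsistency with a possible, not certain, effect on a primary safety endpoint. IAP 15.4 departs from the IAP's own on-treatment period and from the on-treatment summaries planned in the protocol, does so without a statement in IAP 7, and conflicts with its own listing flag.

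Its size is up to 31 − s extra days per subject who starts new therapy within 30 days of last dose, and 33 or 17 percentage points per affected subject in a level of 3 or 6. How often this would happen cannot be judged from the documents; the 5%, 10% and 20% figures are assumptions. All analyses are descriptive, and the dose-escalation model uses dose-limiting toxicities, so what is at risk is the reported laboratory profile by dose level. It merits correction because it is specific and cheap to put right.

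**What to change.** In IAP 15.4, replace the on-study window with the IAP 9 on-treatment period for the worst-grade, shift and endpoint tables, including where the text now refers to any post-baseline visit or to the worst postbaseline grade. Keep later values in the listings, flagged as taken after the start of new therapy. For the eDISH plot, use the same period but show or flag later peaks, because a delayed M4112 liver or immune-related effect is possible. If the wider window is intended, say so in IAP 7 with the reason, and bring the listing flag into line with it.

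The cost is a short text change and reuse of a date already needed for treatment-emergent adverse events. There is one real downside: a delayed M4112 effect first seen after new therapy leaves the summary tables. The IAP already accepts that for adverse events, and the flagged listings and plot keep such values in view.

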#### NCI-CTC grades available:

Shifts from baseline in NCI-CTC grade to the worst postbaseline grade will be summarized separately for hematology and chemistry laboratory parameters. Each summary will be presented by parameter for each dose level and overall.

The categories for worst post-baseline grade are as follows:

- Any higher grade
- Grade 3 or 4
- Grade 4

**NCI-CTC grades not available:**

For parameters where there is no toxicity grade defined, shifts from baseline will be considered from within normal limits to above the upper limit of normal (ULN) or to below the lower limit of normal (LLN).

All CTC gradable and non-CTC gradable parameters will be listed for each measurement. Parameters will be grouped by category. Abnormal laboratory values will be listed.

Listings will include at least the following items:

- Planned dose level
- Subject identification number
- First/last dosing date
- Parameters
- Visit
- Date (treatment day)
- Analysis value
- SI unit
- Change from baseline
- Reference range status (Low, Normal, High)
- CTC grade (with associated CTC name)
- Baseline flag (Yes/No)
- Worst value on-treatment flag (Yes/No)

Laboratory values that are outside the normal range will also be flagged in the data listings, along with corresponding normal ranges. Any out-of-range values that are identified by the Investigator as being clinically significant will be shown in a data listing. These are grade  $\geq 3$  non hematologic toxicities and grade  $\geq 4$  hematologic toxicities.

Subjects without postbaseline laboratory samples will be excluded from analyses with respect to values after the baseline.

**Hepatotoxicity assessment:**

A plot of peak ALT versus peak total bilirubin, both relative to the ULN, will be provided. This eDISH (evaluation of drug-induced serious hepatotoxicity) plot will have reference lines at 3xULN for ALT and 2xULN for total bilirubin. Each subject will get a special character/color combination; the color will represent dose level, and the characters within each color will be used to distinguish the subjects from one another, with ID numbers presented in a legend (sorted by dose level and subject ID number).

## 15.5 Vital Signs

The maximum on-treatment changes from baseline in vital sign measurements will be grouped as indicated in Table 5:

**Table 5 Analysis Categories for Vital Sign Parameters**

Parameters	Categories of Change from Baseline
Body temperature increase	< 1 °C, 1-<2 °C, 2-<3 °C, ≥ 3 °C
Heart rate increase from baseline <100 bpm; ≥ 100 bpm	≤20 bpm, >20 – 40 bpm, >40 bpm
Heart rate decrease from baseline <100 bpm; ≥ 100 bpm	≤20 bpm, >20 – 40 bpm, >40 bpm
SBP increase from baseline <140 mmHg; ≥ 140 mmHg	≤20 mmHg, >20 – 40 mmHg, >40 mmHg
SBP decrease from baseline <140 mmHg; ≥ 140 mmHg,	≤20 mmHg, >20 – 40 mmHg, >40 mmHg
DBP increase from baseline <90 mmHg; ≥ 90 mmHg	≤20 mmHg, >20 – 40 mmHg, >40 mmHg
DBP decrease from baseline <90 mmHg; ≥ 90 mmHg	≤20 mmHg, >20 – 40 mmHg, >40 mmHg
Respiration rate increase from baseline <20 bpm; ≥ 20 bpm	≤5 bpm, >5 – 10 bpm, >10 bpm
Respiration rate decrease from baseline <20 bpm; ≥ 20 bpm	≤5 bpm, >5 – 10 bpm, >10 bpm

For each patient the worst on-treatment value will be calculated. Missing values will define a separate category.

The following summaries will be prepared for vital sign parameters as grouped above considering only subjects with postbaseline values:

- Maximal shifts (changes in categories)
- Listing of highest change per subject

An additional subject data listing will present all changes from baseline reported in the highest categories.

## 15.6 Electrocardiograms

Triplet 12-lead electrocardiogram (ECG) results will be presented in a listing, which will include planned dose level, subject identifier, age, sex, race, study visit and day, date/time of assessment, planned ECG time point, ECG parameter (unit), result, and clinical significance. Parameters to be included are as follows:

- Heart rate (beats/min)
- RR duration (msec)
- PQ/PR duration (msec)

- QRS duration (msec)
- QT duration (msec)
- QTc – Fridericia's correction (msec)
- ECG interpretation (normal vs. abnormal) as assessed by Investigator

Quantitative data for the aforementioned parameters will also be summarized using descriptive statistics, based on the average values of the triplicate measurements.

The incidence and percentage of subjects with potentially clinically significant abnormalities (PCSA) for 12-lead ECG parameters will be summarized during the on-treatment period. The PCSA criteria are provided in [Table 6](#) below.

**Table 6 Potentially Clinically Significant Abnormalities Criteria for ECG**

Test	Potentially Clinically Significant Abnormalities (PCSA) Criteria
Heart Rate (HR)	$\leq 50$ bpm and decrease from baseline $\geq 20$ bpm $\geq 120$ bpm and increase from baseline $\geq 20$ bpm
PR Interval	$\geq 220$ ms and increase from baseline $\geq 20$ ms
QRS	$\geq 120$ ms
QTcF absolute	Interval $\geq 450$ - $< 480$ msec Interval $\geq 480$ - $< 500$ msec Interval $\geq 500$ msec
QTcF change from baseline	Increase from baseline $\geq 30$ - $< 60$ msec Increase from baseline $\geq 60$ msec

QTc will be corrected based on Fridericia's formula ( $QTcF = QT / \sqrt[3]{RR}$ ) where RR=60/HR. Baseline QTcF will be derived from the visit that other ECG parameters are flagged as baseline. If there are multiple assessments at the same visit and time point, the average will be calculated for each parameter and used for the analysis.

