ECG = Electrocardiogram; eCRF = electronic case report form; **CCI** [REDACTED]; **CCI** [REDACTED]; PBMC = peripheral blood mononuclear cell; PD = pharmacodynamics; PK = pharmacokinetics; QTc = corrected QT interval; **CCI** [REDACTED].

- a Including optional metabolite analysis from samples. For all study medication administration, a physician must be present at the site or immediately available to respond to emergencies during all administrations. Critical care and resuscitation facilities should be available immediately.
- b Actual collection times should be collected in the eCRF along with the times of the last dose administration.
- c For subjects in single M4112 dose escalation:  
QTc monitoring: In addition to the ECGs collected for safety monitoring, subjects will undergo replicate (at least 3) digital 12-lead ECGs after a minimum of 5 min rest in the semi-recumbent position on Cycle 1 at Day 1 and Day 15 at -45, -30 and -15 min predose and at 0.5, 1, 2, 3, 4, 6 and 8 postdose. ECG recordings must be performed before PK sampling time points. Time points may change if  $C_{max}$  is not as predicted.
- d Predose = approximately 12 ( $\pm$  4) h post the last evening dose.
- e Predose replicate readings will be collected -45, -30 and -15 min predose; a triplicate digital 12-lead ECG will also be collected predose (within 30 min) for local reading.
- f In addition, standard digital triplicate (within 2 min) 12-lead safety ECGs are to be collected predose and at 2, 3, 4 and 8 h postdose on Days 1 and 15 and predose on Day 8 during Cycle 1, and predose and + 2 h postdose on Day 1 Cycle 2. Safety ECGs will be read locally and **all ECGs should be assessed on the day of collection to determine continued eligibility**. The calculated QTc average of the triplicate 12-lead ECGs must be  $\leq$  450 ms for eligibility. Subjects, in which the calculated QTc average increases to  $>$  500 ms or  $>$  60 ms change over baseline during treatment with M4112, have to interrupt study treatment until further clinical evaluation.  
**ECGs should be repeated if QTc is outside the range until resolution.** To assess the safety and tolerability of the IMP, an ECG can be repeated at the Investigator's discretion at unscheduled visits. Start of resting time, ECG time, and PK sampling time will be recorded in the eCRF. Day 1 and Day 15 triplicate digital ECGs will be also be uploaded for summary statistics, outlier and exposure-QTc analyses.

CCI

CCI

CCI

CCI

CCI

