**Definition of baseline:**

In general, the last nonmissing measurement prior to the first study treatment will serve as the baseline measurement. If an assessment is planned to be performed prior to the first dose of study treatment in the protocol and the assessment is performed on the same day as the first dose of study treatment, it will be assumed that it was performed prior to study treatment administration if assessment time point is not collected or is missing. If assessment time points are collected, the observed time point will be used to determine predose on Study Day 1 for baseline calculation. Unscheduled assessments will be used in the determination of baseline. However, if time is missing, an unscheduled assessment on Study Day 1 will be considered to have been obtained after study treatment administration.

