### 15.6.1 Relationship of QTc Changes to Treatment Exposure

A secondary objective of the protocol was to assess QT prolongation potential by central tendency, outlier analysis and the slope of exposure-QTc analysis. Time-matched ECG readings (3 or more replicates) were to be collected at -45, -30, and -15 minutes predose and at 0.5, 1, 2, 3, 4, 6, and 8 hours postdose, just prior to PK sample collections during Cycle 1 at Day 1 and Day 15 during Part IA (M4112 monotherapy) and uploaded for central ECG reading. ECG readings collected on Cycle 1 Day 8 (predose) and Cycle 2 Day 1 (predose and 2 hours postdose) were also to be uploaded. As the study was terminated early, the following analyses are planned to address the potential relationship of QTc changes to the plasma M4112 exposure, based on the Concentration-QTc Analysis Set:

- The average QTc value at each time point will be plotted for each planned dose level for C1D1, C1D8, C1D15 and C2D1.

- The change from baseline will be calculated as the mean change in QTc at each time point (including C1D1, C1D8, C1D15 and C2D1) minus the mean of 3 predose time points (-45, -30 and -15 minutes) on C1D1 and plotted for each time point (if possible, these will be plotted in a joint plot – change in QTc on the left axis and M4112 plasma concentration on the right axis with time on the x-axis).
- The change from baseline for each time-matched sample will be plotted against the corresponding M4112 plasma concentration for all days and all planned dose levels (combined and separately) in a scatter plot.

Because the data is limited, no linear modeling will be applied.

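### QTcF change from baseline rests on two unreconciled baselines: the last predose time point in SAP Table 6, the mean of three predose time points in Section 15.6.1

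*SAP*

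**What the plan says.** - **SAP Section 15.6 and Table 6.** Table 6 classifies QTcF increases of 30 to under 60 ms and of 60 ms or more. On the baseline, the text says "Baseline QTcF will be derived from the visit that other ECG parameters are flagged as baseline". On replicates, it says "If there are multiple assessments at the same visit and time point, the average will be calculated for each parameter", and the descriptive summaries are "based on the average values of the triplicate measurements".
- **SAP Section 9, definition of baseline.** In general, "the last nonmissing measurement prior to the first study treatment will serve as the baseline measurement". On Day 1, observed assessment times decide what counts as predose.
- **SAP Section 15.6.1.** The change at each time point is taken "minus the mean of 3 predose time points (-45, -30 and -15 minutes) on C1D1". These readings are replicated and intended for central reading: "Time-matched ECG readings (3 or more replicates) were to be collected at -45, -30, and -15 minutes predose".
- **Protocol Table 4, footnotes e and f.** Beside the three predose replicate readings, "a triplicate digital 12-lead ECG will also be collected predose (within 30 min) for local reading". Footnote f adds that "Day 1 and Day 15 triplicate digital ECGs will be also be uploaded for summary statistics, outlier and exposure-QTc analyses".
- **SAP Sections 5.1 and 7.** Section 5.1 maps the secondary QTc endpoint, including central tendency and outlier analyses, to Section 15.6.1. Section 7 drops the concentration-QTc slope analysis and replaces it with summary statistics and scatter plots.

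**The concern.** One subject can have two different QTcF changes at the same time point in one report: one in the outlier table and one in the exposure displays. The outlier part of the endpoint is assigned to a section with no outlier categories. The section that has them uses another baseline and does not say whether the local or the central readings feed it.

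Error in a subject's baseline enters every change for that subject, so a baseline from one time point gives a noisier classification than a mean over three. The protocol treats QT prolongation as an important potential risk. With the slope analysis dropped, these descriptive displays are all the QTc evidence left, so they should agree with each other.

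There is also a wording fault. Section 15.6.1 defines the change as a mean change minus the predose mean. Read literally, that subtracts an absolute QTc value from a difference.

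**Working it through.** The documents give no QTcF variability, expected outlier rate or power for this analysis, so there is no planned figure to reproduce.

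**Step 1. What baseline does Section 15.6 give?** It averages only readings that share a visit and a time point. Section 15.6.1 counts the readings at 45, 30 and 15 minutes before dosing as three time points. Section 9 takes the last measurement before dosing. Together these give a triplicate mean at the last predose time point.

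**Step 2. Noise in the change.** Let s be the within-subject SD of a triplicate-mean QTcF at one time point, m the number of predose time points in the baseline, and ρ the correlation of errors among them.

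Var(change) = s² + s²[(1 − ρ)/m + ρ]

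- ρ = 0: 2.00 s² for m = 1 and 1.33 s² for m = 3. SD ratio = √(2/1.333) = 1.22.
- ρ = 0.5: 2.00 s² for m = 1 and 1.67 s² for m = 3. SD ratio = √(2/1.667) = 1.10.

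**Step 3. One post-baseline time point.** With true mean increase μ, P(change ≥ 30) = 1 − Φ[(30 − μ)/SD]. For s = 10 and ρ = 0, the SDs are 14.1 (m = 1) and 11.5 (m = 3).

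| μ (ms) | one time point | mean of three |
|---|---|---|
| 0 | 1.7% | 0.5% |
| 20 | 24.0% | 19.3% |
| 30 | 50% | 50% |
| 40 | 76.0% | 80.7% |

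**Step 4. Any of 12 time points.** These are the scheduled safety ECGs through Cycle 2 Day 1: four postdose on C1D1, one on C1D8, five on C1D15 and two on C2D1. The shared baseline error is integrated out: P = 1 − E[Φ((30 − μ + bZ)/s)¹²], with b = s√[(1 − ρ)/m + ρ] and Z standard normal. The last column is 24 (the approximate planned Part IA size) times the difference, at ρ = 0.

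| s | μ | one time point | mean of three | shift in 24 subjects |
|---|---|---|---|---|
| 8 | 0 | 3.4% | 0.7% | +0.66 |
| 8 | 10 | 22.3% | 14.1% | +1.97 |
| 8 | 20 | 62.7% | 67.4% | −1.15 |
| 10 | 0 | 11.7% | 4.9% | +1.63 |
| 10 | 15 | 54.1% | 55.4% | −0.31 |
| 10 | 20 | 70.6% | 78.0% | −1.77 |
| 12 | 0 | 22.3% | 14.1% | +1.97 |
| 12 | 20 | 75.4% | 83.8% | −2.01 |

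Over s = 5, 8, 10 and 12 ms and μ from 0 to 30 ms, the shift runs from about +2.0 to −2.0 subjects at ρ = 0, and from about +0.8 to −0.8 at ρ = 0.5. The sign changes between μ = 20 and 30 ms for s = 5, between 15 and 20 for s = 8, and between 10 and 15 for s = 10 or 12.

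**Step 5. The 18 time-matched time points.** These are 7 postdose on C1D1, 1 on C1D8, 8 on C1D15 and 2 on C2D1. With no drug effect and ρ = 0, any increase of at least 30 ms occurs in 0.31% versus 0.01% of subjects (s = 6), 4.6% versus 1.0% (s = 8) and 14.9% versus 7.0% (s = 10). At s = 8 and ρ = 0.5 it is 4.6% versus 2.6%. At s = 8, ρ = 0 and a constant 20 ms rise, the order reverses to 69.1% versus 76.4%, which is 24 × 7.3% = 1.8 subjects.

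**The case against.** The strongest reply is that the plan may describe two datasets, each with its own baseline. Section 15.6 lists the investigator's interpretation and clinical significance, which fits the locally read safety ECGs, and these have one predose triplicate by design. Section 15.6.1 concerns the centrally read replicates. On that view nothing is thrown away. Alternatively, protocol Table 4 has a single nominal predose row. If all three predose readings were coded under it, the averaging rule in 15.6 would pool them and most of the discrepancy would vanish.

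Both readings are possible and neither is stated. Footnote f of protocol Table 4 assigns the uploaded Day 1 and Day 15 triplicates to the outlier analysis, which cuts against a purely local Table 6. So the need to state time points and source remains.

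Four stronger inferences are tempting, and the documents do not support them:
- **The 15.6 baseline is a single reading.** It is at least a triplicate mean.
- **Table 6 discards two of three baseline time points.** That assumes it draws on the central replicates, which is not stated.
- **Local and central readings will be pooled.** The averaging rule does not forbid this, but nothing says that sources are to be combined.
- **Table 6 over-counts 30 ms increases.** This holds only for small true effects. The documents give no SD, and the direction reverses for larger effects.

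It also stands that all analyses are descriptive and that the faulty formula is editorial, since its intent is clear.

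**Conclusion.** The concern holds as a minor point. Sections 15.6 and 15.6.1 define the QTcF change on different baselines without reconciling them, the source of the Table 6 ECGs is unspecified, and the outlier endpoint is mapped to the section without the categories. If Table 6 uses one predose time point, its change is up to 1.22 times as variable as that in 15.6.1. The count of subjects with a 30 ms increase then moves by at most about 2 of 24, upward for small true effects and downward for larger ones.

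This size rests on assumptions outside the documents: normal errors, s from 5 to 12 ms, predose correlation of 0 or 0.5, independent errors across post-baseline time points, and a true effect constant over time. No dose decision depends on Table 6.

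**What to change.** 1. For C1D1, C1D8, C1D15 and C2D1, apply the Table 6 QTcF change categories and the descriptive changes to the central readings. Use the mean of the three C1D1 predose time points as baseline, as in 15.6.1.
2. Add a flagged fallback for subjects with a missing predose time point.
3. Report locally read ECGs, including those from Cycle 4 onward, in a separate table against the local predose triplicate. Do not average local with central readings, and do not combine them in one worst-category count.
4. Correct 15.6.1 so that the change is the QTc at each time point minus the mean of the three C1D1 predose time points.
5. In Section 5.1, map the outlier endpoint to the section that holds its categories.

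The central predose replicates are already in the planned collection. The cost is SAP wording, a fallback rule and one additional table.
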